6.4.1.1 ESSDAI

The ESSDAI is a systemic disease activity index that includes organ-by-organ definitions of disease activity (Seror et al, 2010). The ESSDAI grades disease activity in 12 domains (cutaneous, respiratory, renal, articular, muscular, peripheral nervous system, central nervous system, hematological, glandular, constitutional, lymphadenopathic, and biological). The weights of each domain were obtained by multiple regression modeling, using the Physician's Global Assessment of Activity as gold standard.

Each domain is weighted from 1 (Biologic domain) to 6 (Muscular domain) and has 3 or 4 levels of activity per domain, ranging from 0 (no activity) to 3 (high activity).

The theoretical range of values for the ESSDAI is 0 to 123, with the final score being calculated as follows:

Final Score = Sum of all 12 domain scores Domain score = Activity level × Domain weight

VIB4920

Low activity status is defined as ESSDAI < 5, moderate activity as $5 \le ESSDAI \le 13$ and high activity as ESSDAI ≥ 14 (Seror et al, 2016a). The MR team described in Section 6.1 will confirm disease activity based on ESSDAI at key time points during the study.

6.4.1.2 ESSPRI

ESSPRI is a self-evaluation tool that was developed in a multicenter international cohort of 230 patients (Seror et al, 2011). The ESSPRI uses a 0 to 10 numerical analog scale (ranging from 0 [no symptoms] to 10 [maximal imaginable severity]), one for the assessment of each of the 3 domains: dryness, fatigue, and pain (articular and/or muscular). The weights of the domains are identical, and the mean of the scores of the 3 domains represents the final score. The recall period is stated in each question as "the last 2 weeks." The instrument can be completed in approximately 1 minute.

6.4.1.4 Functional Assessment of Chronic Illness Therapy (FACIT)-Fatigue

The FACIT-Fatigue is a 13-item questionnaire, subject-completed, used to assess the impact of fatigue. Its recall period is 7 days. The responses range from 0 (Not at all) to 4 (Very Much). To calculate the total score, the negatively stated items are reversed by subtracting the response from "4". Final scores are the sum of the responses and range from 0 to 52. Higher scores indicate better QoL. It takes 5-10 minutes to complete.

6.4.1.7 Ocular Surface Disease Index (OSDI)

OSDI is a valid and reliable instrument for assessing effect on vision-related function and dry eye disease severity (normal, mild, moderate, and severe). Its recall period is 1 week. It is composed of 12 questions that the physician asks the subject and circles the number that best represents each question. The responses for each question range from 0 (None of the time) to 4 (All of the time). The OSDI score is calculated as (sum of scores for questions answered)/(number of questions answered)×25, which ranges from 0 to 100 with higher scores signifying greater disability. The assessment can be completed in 5 minutes.

6.4.1.9 Patient Global Impression of Severity

The PGIS is a single item designed to capture the subject's perception of overall symptom severity over the past week on a 5-point categorical response scale (none, mild, moderate, severe, or very severe).

6.4.1.14 ClinESSDAI

ClinESSDAI is a validated SS disease activity index, based on ESSDAI that excludes the biological domain and assigns different weights assigned to each domain. ClinESSDAI was developed in an effort to diminish possible associations between the B-cell biomarkers measured by the ESSDAI biological domain and clinical activity measures (Seror et al, 2016b). The theoretical range of values for the ClinESSDAI is 0 to 135, and similar to ESSDAI, low-activity status is defined as < 5, moderate-activity as $5 \le$ ClinESSDAI ≤ 13 and high-activity as ≥ 14 (Seror et al, 2016a). ClinESSDAI has been validated and shown to correlate well with ESSDAI and is considered a useful tool to detect change independent of biological effect of the drug (Seror et al, 2016b; Dumusc et al, 2018; Quartuccio et al, 2017).

6.4.2 Safety Assessments

Safety assessments will be conducted during the active treatment period according to the assessments shown in Table 2 and will consist of:

- Monitoring and recording all AEs (including AESIs) and SAEs (see Section 8.1 through 8.4 for details)
- Safety laboratory tests (serum chemistry, hematology, and urinalysis [see Section 8.5 for details])
- Concomitant medications
- Vital signs, physical examination (full or symptom-driven depending on the visit), and weight
- ECG
- Urine pregnancy test (for females of childbearing potential)
- Coagulation tests

6.4.3 Additional Disease-related Assessments

The assessments related to SS described in the following sections will be conducted according to the schedules shown in Table 2 (treatment period) and Table 3 (off-treatment period).

[figure not shown]
6.4.3.1 Autoantibody Panel

Serum will be collected to assess the presence of anti-SSA (Ro), anti-SSB (La), antinuclear antibodies, and RF.

6.4.3.2 Inflammatory Markers

Whole blood, plasma, serum, and urine will be collected to assess levels of plasma immunoglobulins (IgM, IgG, and IgA), beta-2 microglobulin, high sensitivity CRP, C3, C4, serum free light chains, cryoglobulins, and serum and urine immunofixation.

6.4.4 Immunogenicity Assessments

Plasma samples for immunogenicity (ADA to VIB4920) will be taken prior to drug administration according to the visits specified in Table 2 (treatment period) and Table 3 (off-treatment period) and assessed using a validated immunoassay.

6.4.5 Pharmacokinetic Assessments

Plasma samples to determine the concentration of VIB4920 will be taken according to the visits specified in Table 2 (treatment period) and (Table 3) (off-treatment period) using a validated assay.

6.5 Off-treatment Period

The off-treatment period will comprise 12 weeks following the last dose of IP and includes Visit 14 and Visit 15 (or EDV in the event of premature discontinuation from the study). All procedures to be conducted at the Off-treatment visits are listed in Table 3.

Efficacy assessments to be conducted at the off-treatment visits will include: Patient Global Impression of Severity, Patient Global Impression of Change, ESSPRI, FACIT-Fatigue, , oSDI, , and . Details on these assessments are presented in Section 6.4.1.

Safety assessments will include: AEs/SAEs, concomitant medications, full or symptom-driven physical examination, vital signs, ECG, weight, and safety laboratory tests. For details of these assessments, see Section 8.

Additional disease-related assessments will be conducted as shown in Table 3 and are described in Section 6.4.3.

The device will be collected at the last patient visit or the EDV, whichever is later (Table 3).

6.6 Discontinuation or Withdrawal

6.6.1 Discontinuation of Treatment

IP must be discontinued if the Investigator determines that continuing it would result in a significant safety risk for that subject. Reasons for study drug discontinuation are or can be:

1. Withdrawal from the study (due to withdrawal of consent or noncompliance with study procedures), as described in Section 6.6.2.

- 2. Withdrawal of consent from further treatment with IP.
- 3. Receipt of restricted medication, as described in Section 7.4.2 for Population #1 and Section 7.4.4 for Population #2.
- 4. Receipt of rescue medication for increased disease activity may lead to discontinuation of IP, as described in Section 7.4.3 for Population #1 and Section 7.4.5 for Population #2.
- 5. AE or significant laboratory abnormality that, in the opinion of the Investigator and/or the Sponsor, warrants discontinuation of further dosing.
- 6. Pregnancy or a decision to become pregnant.
- 7. Any Grade ≥ 3 TEAE that is considered to be related to IP by the Investigator, unless in the opinion of the Investigator, the event(s) are manifestations of SS (eg, within the definitions included in the ESSDAI). Isolated Grade ≥ 3 laboratory abnormalities without a clinical event meeting the above criteria will not automatically lead to discontinuation of IP.
- 8. Any of the following liver function abnormalities:
 - a. ALT or AST $> 8 \times ULN$;
 - b. ALT or AST > 5 \times ULN for more than 2 weeks;
 - c. ALT or AST > $3 \times \text{ULN}$ and bilirubin > $2 \times \text{ULN}$ or international normalized ratio (INR) > 1.5; see Appendix 3 for additional details regarding reporting of subjects with ALT or AST > $3 \times \text{ULN}$ and bilirubin > $2 \times \text{ULN}$ with unknown etiology (ie, Hy's law [HL] cases).
- 9. Anaphylaxis or a serious hypersensitivity reaction attributed to VIB4920.
- 10. Any life-threatening or serious infection or opportunistic infection.
- 11. Malignancy.
- 12. Any other reason when the Investigator determines that continuing IP would result in a significant safety risk for that subject.

Subjects who prematurely discontinue IP before Day 169 will undergo scheduled evaluations until Day 169 visit and at least 3 months of off-treatment follow-up after the last IP administration, at which time they will undergo an EDV. They will not be eligible for treatment during Stage II.

Subjects who prematurely discontinue IP after Day 169, while in Stage II, will undergo scheduled evaluations until the end of the off-treatment period (Day 365) or complete at least 3 months of off-treatment follow-up after the last IP administration, at which time they will have an EDV. An IP discontinuation form should be completed, giving the date and primary reason for stopping study treatment.

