The primary endpoint for Population #1 will be change from baseline in ESSDAI at Day 169. The primary endpoint for Population #2 will be change from baseline in ESSPRI at Day 169. Full lists of the endpoints for Populations #1 and #2 are presented in Section 3.3 and 3.4, respectively.

Within each population, eligible subjects will be randomized to receive VIB4920 1500 mg IV or placebo Q2W x 3 doses, then once every 4 weeks (Q4W) for 4 additional doses (Stage I). Starting on Day 169, subjects randomized to VIB4920 will receive placebo Q4W for 5 doses and subjects randomized to placebo will receive VIB4920 Q4W for 5 doses (Stage II). Subjects who had IP discontinuation will not be eligible for treatment during Stage II. All subjects will be followed for at least 12 weeks after their last dose of IP administration.

A study schematic is presented in Figure 1.

Figure 1 Study Flow Diagram

 Δ = delta; D = days; EoS = End of Study; EP = endpoint; ESSDAI = European League Against Rheumatism Sjögren's Syndrome Disease Activity Index; ESSPRI = in EULAR Sjögren's Syndrome Patient Reported Index; IA = interim analysis; mos = months; PE = primary endpoint.

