4.2 Dose and Treatment Regimen Rationale

The safety, tolerability, and PD effects of multiple IV doses of 1500 mg VIB4920 have been evaluated in RA patients with moderate to severe disease activity.

VIB4920 1500 mg Q2W proved to be efficacious in significantly decreasing disease activity, and clinical improvement lasted through the final visit at 12 weeks after the last dose. Based on PK/PD modeling and biomarker changes observed in the RA patients, the selected dose for this trial is 1500 mg IV Q2W for 3 doses as an induction dose, followed by 1500 mg IV administrations Q4W for an additional 4 doses. Starting at Day 169 of treatment, assignment of subjects will be crossed: subjects randomized to placebo will receive VIB4920 and subjects randomized to VIB4920 will receive placebo in a blinded fashion Q4W for 5 doses. This design has several advantages. First, it provides exposure to VIB4920 to all randomized subjects. Second, omitting the Day 15 induction dose in Stage II allows assessment of the effect of such an induction dose on the rate and magnitude of biologic response and may help optimize the dosing regimen. Third, the longer follow-up of the VIB4920 arms provides an opportunity to better assess the duration of clinical and biologic responses.

No dose-limiting toxicities were identified in the human trials.

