6 STUDY CONDUCT

Subjects will undergo a screening period of up to 4 weeks followed by randomization and treatment for 40 weeks (24 weeks [169 days] for Stage I and 16 weeks [112 days] for Stage II). Subjects will be followed for an additional 12 weeks [84 days] for safety and for assessment of duration of efficacy. The expected full duration of each subject's participation in this study is up to 393 days.

Table 1 summarizes the screening procedures for the study. More than one visit might be needed to complete screening.

The 2016 ACR/EULAR Criteria for Classification of SS are provided in Appendix 1.

 Table 1
 Screening Procedures

Study Period	Screening
Visit Number	V1
Procedure / Study Day	Day -28 to Day -1
Written informed consent	X
SID number assignment	X
Medical history	X
2016 ACR/EULAR Criteria for classification of SS	X
ESSDAI	X
ESSPRI	X
Assessment of prior and concomitant medications	X
Verify eligibility criteria	X
Complete physical examination (including weight and height)	X
ECG	X
Vital signs	X
Assessment of AEs/SAEs	X
Virology: Hepatitis B, C; HIV-1; HIV-2, SARS-CoV-2 ^b	X
TB test (IGRA) ^c	X
Safety Lab Tests: Serum Chemistry, Hematology, Urinalysis	X
Baseline coagulation panel (prothrombin time, PTT)	X
Autoantibody panel (anti-SSA [Ro], anti-SSB [La], ANA)	X
RF	X
Chest X-ray ^d	X
Thyroid Function Tests (TSH, T3, T4, free T4)	X
Pregnancy test (serum β-hCG; females of childbearing potential only)	X
ActiGraph provided to subject (optional)	X

AE = adverse event; ANA = antinuclear antibodies; APL = antiphospholipid; β–hCG = beta-human chorionic gonadotropin; C = complement; ECG = electrocardiogram; ESSDAI = European League Against Rheumatism (EULAR) Sjögren's Syndrome Disease Activity Index; ESSPRI = EULAR Sjögren's Syndrome Patient Reported

VIB4920

Index; HIV = human immunodeficiency virus; IGRA = Interferon Gamma Release Assay; PTT = partial thromboplastin time; RF = rheumatoid factor; SAE = serious adverse event; SID = subject identification; SS = Sjögren's syndrome; TB = tuberculosis; TSH = thyroid stimulating hormone.

- b To participate in study, subjects required a negative SARS-CoV-2 test within 2 weeks prior to randomization.
- c IGRA not required during screening if performed within 12 weeks prior to screening visit with a documented negative result.
- d Chest X-ray not required during screening if performed within 12 weeks prior to screening visit.

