3.5.1.8 Additional analysis

The change from baseline in ESSDAI for population #1 and change from baseline in ESSPRI for population #2 will be analyzed for Stage II + Off-treatment follow-up period based on the cross-over analysis set using the same MMRM model as the primary analysis. Data collected after rescue medications and after discontinuation of study treatment will be included.

The change from baseline in modified ESSDAI excluding peripheral nervous system, central nervous system, and pulmonary domains for population #1 will be analyzed using MMRM approach for Stage I and Stage II + Off-treatment follow-up period based on the full analysis set and cross-over analysis set respectively. The model will include fixed effects for treatment, visit, visit by treatment interaction, and baseline modified ESSDAI score. The handling plan for rescue medication use and treatment discontinuation for Stage I analysis is the same as those for the primary (section 3.5.1.3) and sensitivity (section 3.5.1.5) analyses of the primary efficacy endpoint. Data collected after rescue medications and after discontinuation of study treatment will be included for the Stage II + Off-treatment follow-up period analysis.

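### Protocol 6.6.1 lets subjects who stop study drug in Stage II leave about 3 months later instead of at Day 365, so late duration-of-response visits can be lost, in some cases because response was lost

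*Protocol*

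**What the plan says.** Protocol 6.6.1 has two follow-up rules. Of those who stop IP before Day 169 it says that they "will undergo scheduled evaluations until Day 169 visit and at least 3 months of off-treatment follow-up after the last IP administration". Of those who stop during Stage II it says that they "will undergo scheduled evaluations until the end of the off-treatment period (Day 365) or complete at least 3 months of off-treatment follow-up", counted from the last infusion, with an early discontinuation visit (EDV) at that point. The second rule does not say which of its two end points governs.

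Other sections do not settle it:

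- Protocol 4.1: "All subjects will be followed for at least 12 weeks after their last dose of IP administration". Section 6.5 also counts the off-treatment period as 12 weeks from the last IP dose.
- Protocol 6.8 treats a subject as a completer only after Visit 15, and dates Visit 15 or EDV assessments to Day 365 ± 7 days. Section 6.6.1 permits an EDV well before that.

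The purpose of the follow-up is stated twice. Section 6: "Subjects will be followed for an additional 12 weeks [84 days] for safety and for assessment of duration of efficacy". Section 4.2 lists as an advantage of the design that "the longer follow-up of the VIB4920 arms provides an opportunity to better assess the duration of clinical and biologic responses".

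For the group that starts on active drug, Protocol 4.1 says: "Starting on Day 169, subjects randomized to VIB4920 will receive placebo Q4W for 5 doses".

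SAP 3.5.1.8 applies the primary MMRM to Stage II plus off-treatment follow-up in the cross-over analysis set: "Data collected after rescue medications and after discontinuation of study treatment will be included". SAP 3.5.2.2 plans binary response analyses for the same period. The responder definition in SAP 3.5.2.1, which requires no premature study discontinuation and no rescue, is written for Day 169 and is not restated for Stage II.

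**The concern.** Two features make the *or* matter.

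First, the clock has the wrong origin for the question. In the VIB4920-first group, Stage II IP is saline. Three months from the last IP is then three months from a placebo infusion, which says nothing about how long the effect of VIB4920 lasts.

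Second, exit can depend on outcome. Restricted medication is a listed reason for stopping IP, and rescue for increased disease activity may lead to it. Some of the subjects allowed to leave early may therefore be those who were losing response. Their relapse would be on file, but its later course would not. The Day 309 and Day 365 results would then lean towards subjects who stayed well. The SAP says it will use data collected after discontinuation, yet the protocol lets sites not collect them. Visits that were never made cannot be recovered at the analysis stage.

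**Working it through.** **1. The plan's own timeline.** Protocol 6 says that "participation in this study is up to 393 days". Screening 28 + Stage I 169 + Stage II 112 + off-treatment 84 = 393 days. The last scheduled infusion on Day 281 + 84 = Day 365. Both reproduce.

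**2. Earliest permitted exit.** Infusion days are from Protocol Table 2. Exit = last IP day + 84 (12 weeks) or + 91 (3 months taken as 91 days, an assumption). Follow-up after active drug in the VIB4920-first group = exit − 141; with attendance to Day 365 it is 365 − 141 = 224 days.

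| Last Stage II infusion | Exit, +84 | Exit, +91 | Scheduled visits lost | Days after last active dose, +84 (+91) |
|---|---|---|---|---|
| Day 169 | 253 | 260 | 281, 309, 365 | 112 (119) |
| Day 197 | 281 | 288 | 309, 365 | 140 (147) |
| Day 225 | 309 | 316 | 365 | 168 (175) |
| Day 253 | 337 | 344 | 365 | 196 (203) |

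SAP 3.1.2 bisects the interval between visits, so the Day 365 window opens at about (309 + 365)/2 = Day 337. An EDV after a last infusion on Day 169, 197 or 225 falls before that, so there is no Day 365 value. After a last infusion on Day 253, the EDV falls on the boundary or inside the window and may supply one.

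**3. Effect on the Day 365 mean.** The documents give no rate of Stage II discontinuation or relapse, so every rate below is assumed. Both illustrations cover one arm (VIB4920 first, 400,000 simulated subjects). Errors are in ESSDAI points, in the direction of looking too favourable.

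*Illustration A.* SD 5, correlation 0.7 per visit. Leavers have their last infusion on Day 169, 197 or 225 with equal probability, worsen by 1 point per 28 days up to 6, receive no rescue and exit at 91 days. The mean is estimated under missing at random by sequential regression.

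- 5%, 10% and 20% leavers: error 0.20, 0.41 and 0.80 (at 10%, −3.83 against a true −3.42).
- Immediate 6-point relapse instead of gradual worsening: 0.15, 0.28 and 0.56.
- Day 253 added as a fourth equally likely last infusion: about 0.30 at 10%.
- Last infusions only on Days 225 and 253: 0.14 at 10% with gradual worsening, 0.08 with a step.

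*Illustration B.* Mean change −5 without relapse; between- and within-subject SD 3.5 each (total √(3.5² + 3.5²) = 4.95). Relapse adds 5 points. A given share of those relapsing during dosing stop IP, and exit is at 84 days. Selected rows of the nine run:

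| Relapse per 28 days | Relapsers who stop IP | Early leavers | Error, observed cases | Error, repeated-measures | True ≥4-point response | Observed cases | Leavers as non-responders |
|---|---|---|---|---|---|---|---|
| 3% | 25% | 2.9% | 0.12 | 0.04 | 51.0% | 51.8% | 50.4% |
| 6% | 50% | 10.9% | 0.39 | 0.10 | 44.9% | 47.8% | 42.6% |
| 6% | 100% | 22.1% | 0.91 | 0.26 | 44.8% | 51.6% | 40.2% |
| 10% | 25% | 8.6% | 0.22 | 0.03 | 38.4% | 40.0% | 36.6% |
| 10% | 100% | 34.4% | 1.24 | 0.18 | 38.4% | 47.5% | 31.2% |

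Over all nine rows the repeated-measures error runs from 0.03 to 0.26 and the observed-case error from 0.12 to 1.24. The planned continuous analysis is an MMRM, so the repeated-measures figure is the relevant one. The response rate is about 1 to 9 percentage points too high on observed cases, and about 1 to 7 points too low if leavers count as non-responders.

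**The case against.** A reader might infer something stronger: that subjects who relapse early disappear from the data, and that persistence of effect will therefore be overstated. The documents do not support that.

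- Relapse is not a listed reason to stop IP. Rescue only may lead to stopping, and after restricted medication the Medical Monitor and Sponsor decide whether IP continues (Protocol 7.4.2 and 7.4.4). Most other listed reasons concern safety, pregnancy or consent.
- A relapse that leads to stopping comes before the stop. About 3 months of follow-up after the last IP, and an EDV with ESSDAI and ESSPRI, still take place. What is lost is the later course.
- The larger simulated errors rest on choices that favour the claim: slow worsening that falls largely after exit, no rescue, and no last infusion on Day 253. Protocol 2.1.4.2 reports that response in the RA study held for 3 months after the last dose. If that carried over to this disease and regimen, relapse-driven stops would come later and the error would be smaller.
- The binary results reverse direction if the rule against premature study discontinuation is carried into Stage II.
- Subjects kept to Day 365 after rescue would contribute values affected by rescue, so attendance alone does not give a clean measure of persistence.
- The Stage I *and* protects the Day 169 primary endpoint and does not keep those subjects to Day 365, so the parallel is imperfect. No duration-of-response endpoint appears in the visible text, though the exploratory sections are not shown.

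All of this stands, and it reduces the size of the problem. It does not remove the early exit itself, the mismatch with the stated purpose of the follow-up, or the gap between what the SAP intends to analyse and what sites must collect. Values recorded after rescue can be included or set aside later; values never recorded cannot.

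A reader might also infer a safety shortfall. The rule keeps about 3 months after the last IP, in line with the 12-week minimum in Protocol 4.1, so there is none against the protocol's own standard.

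**Conclusion.** The point holds in a limited form. Protocol 6.6.1 permits Stage II discontinuers to leave before Day 365 at a cost of up to three scheduled visits. In the VIB4920-first group, with a last infusion on Day 169, 197 or 225, it permits 112 to 168 days of follow-up after active drug instead of 224. These figures follow from the schedule with 3 months taken as 12 weeks; at 91 days each is 7 days longer.

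The effect on results is conditional. If some exits follow loss of response, the late continuous scores would tend to look modestly too favourable: about 0.03 to 0.3 ESSDAI points for a repeated-measures estimate, and up to about 0.8 with 20% leavers and slow worsening. These sizes rest entirely on assumed rates and describe one arm's mean, not a treatment difference. The direction for binary response is open, because the SAP does not say how early leavers count.

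Only the Stage II plus off-treatment analyses are touched. The Day 169 primary analysis and its power are not. This is a cheap improvement to make, not a flaw that threatens the trial's main conclusion.

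**What to change.** 1. In Protocol 6.6.1, ask every subject who stops IP in Stage II and remains in the study to attend the scheduled evaluations through Day 365 and for at least 3 months after the last IP, with an EDV only on withdrawal from the study. On schedule this extends nobody beyond Day 365: the latest possible last infusion for a discontinuer is Day 253, and 253 + 91 = 344.
2. Reconcile Protocol 6.5 (12 weeks from the last dose) and 6.8 (Visit 15 or EDV at Day 365 ± 7 days) with that rule.
3. In SAP 3.5.2.2, state how subjects who leave before a given visit, and subjects who were rescued, count in the Stage II plus off-treatment response analyses.

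Cost: at most three already-scheduled visits (Days 281, 309 and 365) for the subjects who stop IP in Stage II, probably few, and a short amendment that needs ethics approval across approximately 70 sites. Treatment, sample size and alpha do not change.
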